9.3 Demographics by race/ethnicity

This is an international study. Since intracranial aneurysms are more prevalent in females than in males, it is anticipated that there will be a higher relative percentage of females represented in the study population.

10 Records and Reports

10.1 Records

Each study site will maintain eCRF and source study records for monitoring and/or audit purposes for the latter of:

- At least five (5) years after study completion; or
- For the period required by the local governing authority and reviewing IRB

These records also include the following:

- Correspondence with the Sponsor, the Funder, the Imaging Core Lab, the DSMB, the steering committee, the various committees and other investigators
- Patient Records, including ICFs and supporting documents in addition to the eCRF
- Most current version of the study protocol with dates and details of reasons for any deviations from the protocol
- Reports of any adverse events, serious adverse event or adverse device effects
- A copy of all approvals related to the clinical investigation
- The approved, blank ICF and blank CRFs
- Certification that the investigational plan has been approved by the IRB from each site
- Signed sub-site agreements with the Sponsor, the site and principal investigator of the site.

The site principal investigator and the study coordinator will be responsible for archiving the data for the periods mentioned above. If the data is to be archived at an off-site, the IRB will be notified and the principal investigator and the study coordinator will be responsible for keeping it confidential. The Sponsor will have full access to this data, and the Funder will have read-only access to this study data, as provided by Northwestern, solely for review and adjudication of information related to any AE, SAE, ADE, SADE and UADE (as defined in section 7.1) for legal and compliance purposes

10.2 Reports

Investigators at participating sites are required to submit reports in conformance with the regulations mentioned throughout this protocol.

10.3 Protocol deviation

Any deviation from the protocol should be reported within 10 days to the Sponsor and clearly documented. Each site will be responsible for reporting any protocol deviation to their IRB according to their institution's standards.

If the investigator finds that the aneurysm characteristics require a deviation from the protocol, he/she must contact the principal investigator of the site as soon as possible and the principal investigator of the site or investigator shall submit a report as to why this decision was made. Any protocol deviation must be clearly documented in the eCRF.

11 Data Management

All required data for this study will be collected on appropriate source medical records and source documents for entry into the EDC within 5 days of the subject visits. A database lock timeline will be created to ensure proper and timely collection of data from all sites (this will be done every 3 months).

12 Monitoring of the study and Quality Control

12.1 Medical Monitoring by DSMB

All SAEs and ADEs will be reported to and evaluated by the DSMB members for a potential relationship to the study device or procedure as set forth in Section 7.2. All AEs will be evaluated by the investigational site and the principal investigator of the site, and they will follow site specific IRB procedure with respect to AEs. The principal investigator of the site will complete the eCRF and notify the Sponsor and Principal Investigator with respect to AEs in accordance with Section 7.

12.2 Data Collection and Monitoring

Each site's study coordinator will collect and document data in hospital and clinic charts. eCRF data will be entered in anonymous form into the secure web-based and password-protected database within 5 days of each subject study visit. Only the investigator, study coordinator and other designated authorized research personnel will have access to the database. Each participating site will have access to only its own data. In addition, the Sponsor, the Principal Investigator, monitor and the study coordinator of the Sponsor's site will have access to the entire database with full rights to act as the administrator of the database.

Data verification occurring during monitoring visits will involve the review of the subject's medical record (for study specific visit dates only) and source documents. These source documents should only be used in instances where the subject's medical record does not contain the data required for study. These forms should be signed and dated by study personnel collecting the data at the time of collection.

Completed eCRFs in final form may be printed and filed in hardcopy for archiving if required by the local governing authority. All data will be exported and stored on appropriate electronic media by the Principal Investigator and to study biostatistician for analyses.

The Principal Investigator of each site is responsible for data integrity at the site and will review and electronically sign all Patient Selection, Adverse Event, Protocol Deviation, Imaging and Study Exit eCRFs.

The clinical site will be monitored routinely by the Sponsor and by a trained study coordinator and/or monitor for adequate enrollment, timeliness of data submission, and compliance with the investigational plan and applicable local and federal regulations. If the site in question fails to show compliance with the above mentioned, the site investigator will be contacted by the principal investigator, and if corrective actions are not taken to resolve the issues, the clinical site may be withdrawn from the study.

12.3 Site Compliance / Deviations

In order to optimize correct and detailed records, all eCRFs should be entered in the web-based database as indicated in Table 6.

In some cases, a site investigator may want to include and randomize a potential Subject who meets all but one Inclusion/Exclusion criterion. The investigator will present the case and report their medical opinion to the Sponsor, Principal Investigator and, if appropriate, the DSMB for consideration. If the prospective deviation is approved then the Subject may be enrolled in the study. This protocol deviation will be documented in the subject's eCRF.

13 Financial and Insurance Matters

As all devices used in this trial are FDA or HPB approved, the coiling procedures are considered Standard of Care and shall be the patient's responsibility (insurance or self-pay). Any follow-up assessments that are protocol driven and not standard of care shall be covered under study agreement.

References

White et al. 2008 (HELPS)	Randomized Controlled trial	495 (249 randomized to the Hydrogel group)	Mean: 6.5 mm 2 - 4.9 mm: 42 5 - 9.9 mm: 144 10 - 24.9 mm: 63	139 vs. 110	-	47.3%	31.3% (near-complete)	21.4%	-
Gunnarsson et al. 2009	Retrospective	200	S (<10mm): 125 L (10 - 25 mm): 75	104 vs. 96	-	53.8%	29.6%	16.6%	58%

Table 2. Major Hydrogel coil studies - follow up results

Author and year	Complications/ Morbidity	Mortality	% followed up	Mean Follow-up (Months)	Recanalization	Retreatment
Berenstein et al. 2006	14 / 5.8% Immediate post-procedure Morbidity	0% (Immediate post-procedure)	51%	10.3	21%	-
Cloft et al. 2007 (HEAL)	10.9% (Immediate post-procedure)	-	135/191 (70.6%)	3-6	28.1%	-
Gaba et al. 2006	4%	2 (4.4 %)	84%	12.3	17%	10%
Deshaies et al. 2007	32.8%	-	90%	12	15%	-
Fanning et al. 2007	12% / 6.4% morbidity	1.1%	63%	7.5	14.3%	4.8%
Kang et al. 2007	16 procedure related-events	0%	68%	≥ 6 mo: 54 aneurysms ≥ 12 mo: 13 aneurysms	11%	-
White et al. 2008 (HELPS)	70 (Procedural Adverse events)	3.6%	-	-	-	-
Gunnarsson et al. 2009	15% complication (6% leading to permanent morbidity or mortality)	-	60.5%	16.3	21.5%	10.7%

Table 3. Hunt and Hess classification of SAH

Grade	Description
1	Asymptomatic, or mild H/A and slight nuchal rigidity
2	Cr. N. palsy (e.g. III, VI) moderate to severe H/A, nuchal rigidity
3	Mild focal deficit, lethargy, or confusion
4	Stupor, moderate to severe hemiparesis, early decerebrate rigidity
5	Deep coma, decerebrate rigidity, moribund appearance

Add one grade for serious systemic disease (e.g. HTN, DM, severe atherosclerosis, COPD) or severe vasospasm on arteriography.

Table 4. Schedule of assessment

HydroCoil Embolic System Clinical Trial	Screening & Baseline	Procedure	Post-procedure Follow-up	Immediate Follow-Up	Early Follow-Up	Final Follow-Up
Schedule of Events	Up to 30 days prior to surgery	Day 0	Day 1	3-28 Days	3-12 Months	18-24 Months
Review Inclusion/Exclusion	X					
Data Entry, Validation, Query Resolution	X	X	X	X	X	X
Obtain Informed Consent	X					
Randomization		X				
Adverse Events		X	X	X	X	X
Demographic Data	X					
Medical History	X					
Hunt & Hess Scale ¹	X	X	X			
Modified Rankin Score	X	X	X	X	X	X
NIH Stroke Scale (NIHSS) ¹	X	X	X		X	X
SF-36	X ³				X	X
Angiogram	X	X			X	X
MRA	X ²				X ²	X ²
Final Visit Assessment						X

¹ For Subjects enrolled with ruptured aneurysms² According to standard of care of each institution.³ For Subjects with ruptured aneurysms who are unable to complete the SF-36 prior to procedure, the SF-36 can be completed prior to subject discharge following procedure.

Table 5. Effect Sizes for outcomes with N=600, with 80% power

Outcome	baseline (platinum) rates	Hydrocoil rates	% change
Recurrence	33.0%	22.8%	-30.9%
Complete occlusion	55.6%	66.7%	20%
	47.6%	59.0%	23.9%
Complete or nearly complete occlusion	85.5%	92.6%	8.4%
Retreatment	17.4%	9.6%	-44.8%

Table 6. Electronic Data Entry Timelines

eCRF	Timeline
Adverse Event eCRF	
In the event of a serious adverse event, complete the AE CRF on the web-based database and fax report within 24 hours of learning of the event to the Sponsor and Funder. Comply with local reviewing IRB reporting rules.
 
In the event of an unanticipated adverse device effect, complete the AE CRF on the web-based database and fax report as soon as possible, but no later than 10 working days after the investigator first learns of the effect to the Sponsor and Funder. Comply with local reviewing IRB reporting rules.

All other eCRFs	Within 5 business days of subject discharge or follow-up

Table 7: Required Imaging Schedule

HydroCoil Embolic System Clinical Trial	Screening & Baseline	Surgery		Post-Procedure Follow-up	Immediate Follow-up	Early Follow-up	Final Follow-up
		Pre-Coil	Post-Coil				
Schedule of Events	Up to 30 days prior to surgery			Day 1	3-28 Days	3-12 Months	18-24 Months
Angiogram		X	X			X	X
MRA						X ²	X ²

² According to standard of care at each institution

Please note that if an angiogram, MRA or CTA is performed 30 days before surgery, the Imaging eCRF should be completed and the CD shipped to the core lab and Northwestern University. This imaging is optional and is not required for the study.

Results of MRIs or CTs are not needed

Figure 1. Aneurysm occlusion grading system as reported by Meyers et al.²³

[figure not shown]

Figure 2. Raymond angiographic classification of residual coiled aneurysm.

[figure not shown]

Figure 3: Classification of Adverse Events

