4.4 Safety Outcomes

- Peri-aneurysmal edema
- Aseptic meningitis
- Thromboembolic events
- Vasospasm
- Ventricular Enlargement
- Hydrocephalus
- Aneurysm Rupture
- Parent Vessel Occlusion

5 Clinical Study Design

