6.2 Baseline Assessments (up to 30 days prior to procedure)

The following information will be assessed and documentation will be maintained as source records at the study site:

- Neurological assessment of the subject and evaluation of symptoms will be performed by an experienced neurosurgeon, neurointerventionalist or authorized designee. In the case of a ruptured aneurysm, the severity of symptoms is to be administered and assessed by authorized and certified research staff using both the National Institutes of Health Stroke Scale (NIHSS) and the Hunt and Hess scale (Table 3)..
- The Subject's modified Rankin Scale (mRS) assessment score will also be collected for the eCRF to reflect baseline functional status
- SF-36 questionnaire to assess general quality of life (for ruptured cases when the subject is impaired and unable to complete the SF-36 questionnaire, this can be completed by the subject prior to discharge)
- Medical History
- Current medications history including anti-platelet and anti-coagulation drugs
- Physical Examination
- Laboratory values to include hemoglobin (Hg), platelet count (Plt), prothrombin time (PT), partial thromboplastin time (PTT), international normalized ratio (INR), and creatinine (Cr). A pregnancy test is required if the subject is female with child-bearing potential. Any female of child-bearing potential who has not been diagnosed with menopause or any other clinical condition that would prohibit conception and/or has not undergone any kind of surgery that would prohibit conception (e.g. total hysterectomy or bilateral oophorectomy) should receive a pregnancy test prior to enrollment.
- A CT scan or MRI may be used to evaluate study Subject eligibility. However, this imaging is not required to be recorded on the eCRF nor is the imaging CD required to be sent to the Imaging Core Lab or Sponsor.

Once the consent form has been signed, all subjects should complete the baseline assessments discussed in Section 7.2 and the Schedule of Assessments (Table 4).

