6.2.1 Clinical and radiographic evaluation

A pre-treatment clinical assessment will be performed by the treating physician or designee and a mRS score should be obtained. The NIHSS and Hunt and Hess scale scores will be recorded for those patients presenting with ruptured aneurysms and/or SAH. The patient's medical co-morbidities will also be recorded for study analysis. Results of a pre-embolization brain angiography, MRA or CTA may be recorded and submitted to the Imaging Core Lab and Sponsor if imaging was performed within 30 days prior to enrollment (optional). Measurement of the three (3) aneurysm dimensions of interest (height, length, and width), its neck size and maximal diameter will be recorded as well as any additional relevant radiographic features (e.g. partial thrombosis, peri-aneurysmal edema, etc.).

For conventional angiography, two 10 mm silicon-coated spherical ball bearings must be used for each enrolled subject during procedural angiography (immediately pre- and post-coiling) as well as during any subsequent follow-up angiograms to make measurements as standardized as possible. One ball bearing will be placed on the forehead and the second in the periauricular area ipsilateral to the aneurysm. Image intensifiers will be placed as close to the head as possible. A 4-axis orthogonal view of the aneurysm will be obtained.

Imaging data will be recorded on the Imaging eCRF. Imaging CDs will be sent to the Imaging Core Lab and the Sponsor, Northwestern University. In the event ball bearings are not used during procedural angiography, the Sponsor may require submission of baseline imaging including CTA or MRA to enable the Imaging Core Lab to more accurately obtain measurements.

Please see Table 7 which outlines the imaging schedule.

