6.8 Immediate follow-up visit: Between 3 to 28 Days post-coiling

The immediate post-coiling follow-up will consist of a clinical assessment and specifically a neurological exam. This visit involves a mRS assessment for all subjects and NIHSS and Hunt & Hess scale assessments for subjects presenting with a ruptured aneurysm. The investigator or an authorized member of the research team will assess for any new or unresolved adverse events. The need for cerebral imaging will be assessed and performed according to the standard of care at each institution to evaluate aneurysm occlusion and to study the early recanalization rate. If the length of hospitalization post-procedure equals or exceeds 3 days, then the 3 to 28 day follow-up will also be considered as the discharge follow-up and it will be marked as such on the eCRF. If a 3-28 day visit is not standard of care at a site, the mRS score and review of adverse events can be obtained via phone.

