6.11 Unscheduled Follow-up Visit

Should an unscheduled follow-up visit occur, the reason for the visit should be clearly marked in the eCRF. In the event there is a change in the clinical neurological status due to an adverse event/serious adverse event, the mRS score should be assessed and entered in the eCRF. If the subject presents with a hemorrhage, the NIHSS and Hunt and Hess scores should be assessed and entered in the eCRF. The investigator or an authorized member of the research team should assess and report any unresolved or new adverse events. If imaging is ordered to assess occlusion or recurrence of the aneurysm, the Imaging eCRF must be completed and the imaging CD should be sent to the Imaging Core Lab and the Sponsor, Northwestern University. If imaging is performed for purposes other than to assess occlusion or recurrence, the Imaging eCRF does not need to be completed and no CD is required for submission.

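### Peri-aneurysmal edema, ventricular enlargement and hydrocephalus are safety outcomes, but no brain CT or MRI is scheduled and recording of routine scans is waived, so they rest almost wholly on selective adverse-event reports

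*Combined protocol and SAP*

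**What the plan says.** Section 4.4 of the protocol names "Peri-aneurysmal edema", "Ventricular Enlargement" and "Hydrocephalus" as three separate safety outcomes.

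The imaging rules are these:

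- **Schedule (Tables 4 and 7).** Angiogram and MRA are the only imaging rows. No brain CT or parenchymal MRI is scheduled at any visit.
- **Note under Table 7.** "Results of MRIs or CTs are not needed". It follows a sentence about imaging before the procedure and names no visit.
- **Baseline (6.2).** A CT or MRI may be used to judge eligibility, but "this imaging is not required to be recorded on the eCRF nor is the imaging CD required to be sent".
- **Baseline features (6.2.1).** Aneurysm dimensions are recorded together with "any additional relevant radiographic features (e.g. partial thrombosis, peri-aneurysmal edema, etc". The imaging named there is angiography, MRA or CTA, and its submission is optional.
- **3 to 28 days (6.8).** "The need for cerebral imaging will be assessed and performed according to the standard of care at each institution to evaluate aneurysm occlusion". Early recanalization is the other stated purpose.
- **Unscheduled visits (6.11).** "If imaging is performed for purposes other than to assess occlusion or recurrence, the Imaging eCRF does not need to be completed". Submission of the CD is waived as well. The same section asks staff to report new or unresolved adverse events.

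On adverse events, 7.2 restricts eCRF capture to events related to the procedure, the device or a change in neurological status, in both arms. Table 4 starts collection at the procedure and continues it to the final visit.

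**The concern.** Edema around the aneurysm and ventricular enlargement are imaging findings. Listing ventricular enlargement apart from hydrocephalus suggests that the imaging sign itself was meant to count, and not only the clinical diagnosis. The plan does not schedule the imaging that would show these findings systematically, and it waives the results where routine care produces them.

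Two things are at stake. First, a by-arm table with few events and no difference could reflect incomplete collection and still be read as reassurance about the hydrogel coils. Second, hydrocephalus can already be present after a subarachnoid hemorrhage. If ventricular status before coiling need not be recorded, there is no imaging record against which to confirm that a case reported later is new.

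**Working it through.** No figure in the plan needs reproducing: Table 5 gives detectable effects for recurrence, occlusion and retreatment only, and Section 9 claims no power for a safety outcome. The check is to trace each outcome through the collection rules.

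| | Edema | Ventricular enlargement | Hydrocephalus |
|---|---|---|---|
| Listed in 4.4 | yes | yes | yes |
| Brain CT/parenchymal MRI scheduled (Tables 4, 7) | no | no | no |
| CT/MRI results required at any visit | no | no | no |
| Named baseline recording item (6.2.1) | yes | no | no |
| Named follow-up recording item | no | no | no |
| Listed as expected risk (7.3) | no | no | yes |
| Can enter as an adverse event (7.2) | if in scope | if in scope | if in scope |

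**Follow-up.** For all three outcomes the adverse-event form is the only named route after the procedure. A silent finding does not change neurological status, so under 7.2 it qualifies only if the site attributes it to the procedure or device. The site placed the coils and knows the arm. The reader described as blinded to coil type is the core lab (6.5), and it need not receive these scans.

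**Baseline.** Edema has a recording instruction, but with no follow-up counterpart it cannot by itself show new edema. Ventricular status has no baseline instruction. This matters for ruptured aneurysms, which are eligible under 5.3.2. As a guide to how common they may be, the hydrogel group of the earlier randomized trial in Table 1 had 139 ruptured and 110 unruptured aneurysms: 139 / (139 + 110) = 139/249 = 55.8%. That is another trial's mix, not a forecast for this one.

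**Effect of incomplete capture.** Let *p_H* and *p_P* be the true event rates in the hydrogel and platinum arms, and *c_H* and *c_P* the fractions of events recorded.

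- Observed difference = *c_H·p_H* − *c_P·p_P*.
- If capture is equal (*c_H* = *c_P* = *c*), this is *c*(*p_H* − *p_P*). The absolute difference shrinks by the factor *c*. The rate ratio is preserved, but rests on fewer events.
- If capture differs by arm, which is possible where the reporter knows the arm, the bias can go either way.

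The documents give none of these four quantities. Tables 1 and 2 report no rate for the three outcomes. A power figure would therefore rest entirely on assumed inputs, and none is offered.

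**Analysis.** Section 9.2 gives these outcomes no definition or denominator. At most they fall under the general reference in 9.2.2 to other binary outcomes.

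**The case against.** The strongest reply is that this is a post-market trial of approved devices in which both arms are standard of care, and that limiting adverse-event capture was deliberate. Adverse events are reviewed at every visit from the procedure onward. A device- or procedure-related event need not be symptomatic to qualify. Reports carry a date, narrative and duration. SAEs and ADEs go to the DSMB (12.1), and imaging can be supplied to the committees on request (7.2). Medical history and neurological status are recorded before treatment, and 6.2.1 names edema as a baseline feature.

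Most of this stands, and it rules out three stronger readings that a reader might infer:

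- **That sites are told not to record CT/MRI findings.** The Table 7 note, 6.2 and 6.11 waive a requirement; none forbids recording. Section 6.11 lifts only the Imaging eCRF and CD at unscheduled visits, not the duty to report adverse events. The Table 7 note can be read as covering follow-up but does not say so.
- **That counts will be close to zero.** Recognized events within the scope of 7.2 can still be reported. What follows is an undercount of unknown size.
- **That old and new hydrocephalus cannot be told apart.** Event dates, narratives and medical history help. What is missing is a required baseline ventricular status to confirm the distinction.

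The reply does not close the gap. Review on request is not systematic ascertainment, attribution of a silent finding is left to an unblinded site, and the baseline edema item has no follow-up match.

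**Conclusion.** The point holds as a mismatch between stated outcomes and stated collection rules. None of the three outcomes has a scheduled brain CT or parenchymal MRI, none has required CT/MRI results, and one of the three has a baseline recording item. Otherwise they depend on adverse-event reports of restricted scope from sites that know the arm. Clinically silent cases may be undercounted, by an amount the documents do not allow anyone to estimate. A finding of no difference between arms would not be evidence about imaging-detected edema or ventricular enlargement.

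This rests on two assumptions: that these outcomes are meant to be compared by arm, as their listing in 4.4 implies, and that some cases are silent or not attributed to the procedure or device. The primary endpoint is not affected. This is a correctable gap in safety ascertainment and should be fixed.

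**What to change.** Reconcile the Table 7 note, 6.2 and 6.11 with 4.4 and 6.2.1:

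1. On the baseline eCRF and each follow-up eCRF, ask whether a routine-care brain CT or MRI was done since the last visit (at baseline, since presentation). If so, record its date and whether peri-aneurysmal edema, ventricular enlargement and hydrocephalus were each present or absent. No extra scan is required.
2. Reword the three waivers so that they no longer cover these items.
3. In Section 9, define a new event as one recorded after the procedure and not present at baseline, and identify subjects whose baseline status is unknown. Report new events by arm among all randomized subjects, split by rupture status.
4. Show the number scanned per arm, and the rate among those scanned, as supportive only. Scanning is a post-randomization choice by physicians who know the coil type, so a comparison restricted to scanned subjects is open to selection bias.

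If the sponsor declines, restate 4.4 so that these outcomes are compared only as clinically reported adverse events, and say in the analysis section that the absence of a difference will not be interpreted as evidence on imaging-detected edema or ventricular enlargement.

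The cost is a few eCRF items, changes to three sentences, a short analysis paragraph and modest extra data entry. Routine scans will still be obtained selectively, so ascertainment improves but does not become complete.
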